### **3.3 Allocation to Interventional Group**

Participants who meet all eligibility requirements, provide a baseline stool sample, and complete 5 to 7 days of sCDAI online surveys, will be randomly assigned to one of the study diets in a 1:1 ratio of SCD:MSD. The randomization will be stratified based on whether the participant is currently using a biologic therapy for CD. As such, there will be two strata as follows:

Biologic Therapy
Yes
No

Randomization will be blocked using variable block sizes ranging from 2 to 4. A study biostatistician at the DCC will generate the randomization scheme which will be incorporated into the study data management system. Once the randomization form is completed in the data management system it will generate the participants' study diet assignment.

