**Analysis of secondary outcomes (Secondary Aim 2):**

The secondary outcomes of clinical remission as assessed by the CDAI, PRO2, PRO3 reduction of hsCRP by >50% and to <5 mg/L, reduction of FCP by >50% and to a value of <250mcg/g and combined clinical remission and resolution of inflammation will be analyzed using the same methods described for the primary outcomes.

The secondary outcomes of fatigue, sleep quality, social aspects and pain interference will be measured using PROMIS short forms using the same methods as previously employed within CCFA Partners. PROMIS items are calibrated using a T score such that 50 is the mean for the general US population with a standard deviation of 10. Higher scores reflect greater level of the domain. We will compare PROMIS scores at baseline and at the end of the trial using a t-test. If there are meaningful differences in baseline scores between the treatment arms, comparison of the PROMIS measures at the end of follow-up will be adjusted for the baseline value using linear regression.

**Analysis of data from weeks 7 – 12 (Secondary Aim 3):** After week 6, participants will need to provide for the meals on their own if they choose to remain on the diet. This provides an opportunity to further assess the combined feasibility of the diets in the real world and patients' satisfaction with following the diet. Utilizing results from 24-hour dietary recalls, we will determine the proportion of patients assigned to each arm who elect to remain on the diet through week 12. We will also determine the proportion of patients who were able to discontinue steroid use by week 12 among the subgroup who were taking steroids in weeks 1-6. Finally, we will assess reasons for discontinuation of the diet among those who did not continue. Comparisons will be made using the CMH test following the principle of intention to treat. The analysis will be repeated among the subgroup of participants who achieved remission by week 6. These results will be qualitatively compared to the free text data on satisfaction and personal experience with the diets.

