## 5.2. Sample size

The study is designed to enroll 97 patients into each of the treatment arms. Specific aims 1 and 2 will be considered separately and no reduction in type 1 error will be applied for multiple testing. The anticipated remission rate in the group receiving the MSD is unlikely to exceed 40% given the historical remission rates in placebo arms of Crohn's disease trials and assuming only a modest therapeutic benefit of this less restrictive of the two diets. Sample size calculations assume no loss to follow-up since all participants who are lost to follow-up will be categorized as non-responders in the analyses of both dichotomous primary outcomes (symptomatic remission and reduction in mucosal inflammation). Our PPRN Patient Governance Council met and determined that the minimum clinically important difference in remission rates is 20% as smaller differences are unlikely to justify the challenges of following a strict restriction diet such as the SCD. Thus, we used an anticipated remission rate of 40% with the MSD and 60% with the SCD to determine the sample size. With 97 participants per group, the study will have 80% power with a type 1 error of 5% to detect a difference of 40% vs 60% in effectiveness of the two diets using a chi test.

In reality, we anticipate that the remission rate in the MSD will be less than 40%. The power curve shown below depicts the power to detect a 20% difference based on the remission rate in the MSD arm of the trial where  $p_1$  represents the remission rate in the SCD arm (i.e.,  $p_1=0.3$  represents power to detect a difference of 10% vs 30% across a sample size ranging from 60 to 120). With 97 participants per group, there is more than 90% power to detect a difference of 10% vs 30% and 80% power to detect a difference of 40% vs 60%.

Finally, all of the power estimates are likely slight under estimates. We expect even more power when the Cochran-Mantel-Haenszel (CMH) chi test is used since we expect that the odds ratios in different strata are in the same direction.

Viewed alternatively, with 97 participants per arm, there is 80% and 90% power to detect the following differences based on the effectiveness of the control diet (i.e. the MSD).

Proportion of MSD group achieving the outcome	80% power to detect an absolute difference (SCD - MSD) greater than or equal to	90% power to detect an absolute difference (SCD - MSD) greater than or equal to
10%	15%	18%
20%	18%	21%

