### **5.5. Efficacy Analysis**

Analysis of the primary outcome: The primary outcomes will be measured at 6 weeks after the start of the study diets. The primary analyses for the RCT will use 2-sided tests of statistical significance and will be performed using the intention-to-treat principle. Thus, patients will be classified according to the study arm that they were assigned, regardless of the amount of food from the assigned diet consumed.

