Analysis of secondary outcomes (Secondary Aim 1): hsCRP data will be analyzed in the same manner as FCP data.

Analysis of secondary outcomes (Secondary Aim 2): The secondary outcomes of clinical remission as assessed by the CDAI, PRO2, PRO3 and combined clinical remission and resolution of inflammation will be analyzed using the same methods described for the primary outcomes. We will compare PROMIS scores at baseline and at the end of the trial using a t-test. If there are meaningful differences in baseline scores between the treatment arms, comparison of the PROMIS measures at the end of follow-up will be adjusted for the baseline value using linear regression.

Analysis of data from the Extension Phase (Secondary Aim 2): After week 6, participants will need to provide for the meals on their own if they choose to remain on the diet. This provides an opportunity to further assess the combined feasibility of the diets in the real world and patients' satisfaction with following the diet. Utilizing results from 24-hour dietary recalls, we will determine the proportion of patients assigned to each arm who elect to remain on the diet through week 12. We will also determine the proportion of patients who were able to discontinue steroid use by week 12 among the subgroup who were taking steroids in weeks 1-6. Finally, we will assess reasons for discontinuation of the diet among those who did not continue. Comparisons will be made using Fisher's exact test following the principle of intention to treat. The analysis will be repeated among the subgroup of participants who achieved remission by week 6. These results will be qualitatively compared to the free text data on satisfaction and personal experience with the diets.

Change from baseline stratified by treatment arm: For continuous outcome measures, such as sCDAI, PRO2, PRO3, and FCP, we will compare the week 6 and week 12 values to the baseline value using the Wilcoxon sign rank test, a nonparametric paired test. These analyses will be conducted separately for each treatment group. Imputation of missing data for this analysis will assume that the worst case scenario that the outcome measure was worse during follow-up than at baseline. (Note that approach to missing data for other analyses are described below).

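### Protocol 8.4.2 names the CMH test and SAP 5.5.2 names Fisher's exact test for the same weeks 7–12 comparisons; the plan should name one.

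*Combined protocol and SAP*

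**What the plan says.** Two current texts describe the same analysis of weeks 7–12 in nearly the same words. Both cover the proportion remaining on the assigned diet through week 12 (secondary objective 4), the proportion stopping steroids by week 12 among those taking them in weeks 1–6, and the reasons for stopping the diet. They differ in the test:

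- Protocol 8.4.2, weeks 7–12 paragraph: "Comparisons will be made using the CMH test following the principle of intention to treat".
- SAP (Appendix G) 5.5.2, Extension Phase paragraph: "Comparisons will be made using Fisher's exact test following the principle of intention to treat".

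On allocation, protocol 3.3 says "The randomization will be stratified based on whether the participant is currently using a biologic therapy for CD", which gives two strata.

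The SAP uses CMH for symptomatic remission and for reduction of inflammation, and carries the same methods over to the CDAI, PRO2, PRO3 and combined outcomes. SAP 5.2 expects CMH to have more power than the plain chi-square test. Protocol 8.4 says that a separate analysis plan will be written and that its own sections summarise it. No rule of precedence is given.

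**The concern.** With two tests specified for one comparison, the analyst must choose, and the choice can decide whether a result falls below 5%. For example, if 39 of 97 in one arm and 53 of 97 in the other continue the diet, Fisher's test gives p = 0.061 and the uncorrected chi-square gives p = 0.044. The trial is open label, and under SAP 3.3 the lead analyst has the raw data during the trial and prepares files by arm for the DSMB.

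The SAP's choice is also the odd one out. It sets aside the stratification factor, departs from the method used for the other binary efficacy outcomes, and runs below its nominal error rate. At stake are consistency and a few points of power on a stated secondary objective. The primary analysis is not affected.

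**Working it through.** **Inputs from the documents.** 97 per arm and 80% power at 5% (SAP 5.2: "With 97 participants per group, the study will have 80% power with a type 1 error of 5% to detect a difference"); 40% v 60% (SAP 5.2: "Thus, we used an anticipated remission rate of 40% with the MSD and 60% with the SCD to determine the sample size"); two-sided testing, stated for the primary analyses (SAP 5.5); 1:1 allocation within two strata (protocol 3.3).

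**Assumptions.** No rates, effect size or power are stated for the weeks 7–12 outcomes, so 40% v 60% is borrowed from the primary outcome. The documents give neither the share of patients on a biologic nor how strongly biologic use predicts these outcomes. I take 30% or 50% on a biologic, a biologic–outcome odds ratio of 1 to 5, and a common treatment odds ratio across strata.

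**Step 1: the plan's own figure.** With pooled rate 0.5,

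power = Φ{[0.20·√97 − 1.96·√(2·0.5·0.5)] / √(0.4·0.6 + 0.6·0.4)} = Φ{(1.9698 − 1.3859)/0.6928} = Φ(0.843) = 80.0%.

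This reproduces the stated 80%.

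**Step 2: the cost of Fisher's conservatism.** Summing exact binomial probabilities over all 98 × 98 possible outcomes at 97 per arm:

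| True rates | Fisher | Chi-square, uncorrected |
|---|---|---|
| 40% v 60% (power) | 76.4% | 80.7% |
| 20% v 40% (power) | 83.4% | 87.0% |
| 40% v 40% (actual size) | 3.4% | 4.9% |
| 50% v 50% (actual size) | 3.7% | 5.2% |

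Both tests here are unstratified, so the 4.2-point difference at 40% v 60% (80.67 − 76.43) has nothing to do with the stratum.

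**Step 3: the cost of dropping the stratum.** Simulated power at 40% v 60%, 200,000 runs per setting. Where two figures are shown, they are for 30% and 50% on a biologic.

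| Stratum odds ratio | Fisher | Chi-square, unstratified | CMH, uncorrected | CMH, corrected |
|---|---|---|---|---|
| 1 | 76.6 | 80.8 | 80.8 | 76.6 |
| 2 | 76.8 / 76.9 | 81.0 / 81.2 | 81.1 / 81.2 | 76.9 / 77.0 |
| 3 | 77.1 / 77.3 | 81.4 / 81.5 | 81.9 / 82.4 | 77.8 / 78.3 |
| 5 | 77.9 / 78.1 | 82.2 / 82.5 | 84.7 / 85.8 | 80.8 / 82.0 |

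- Uncorrected CMH minus Fisher: about 4 to 5 points for odds ratios 1 to 3, and 7 to 8 points at 5.
- Uncorrected CMH minus unstratified chi-square, which is the stratum's own contribution: about 0 at odds ratios 1 to 2, 0.5 to 0.9 at 3, and 2.5 to 3.3 at 5.
- Corrected CMH minus Fisher: about 0 at odds ratios 1 to 2 and about 1 point or less at 3.

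**Step 4: the steroid subgroup.** Its size is not given. For an assumed 15, 20, 30 and 40 per arm at 40% v 60%, Fisher has 9.5%, 14.3%, 25.7% and 36.9% power; the unstratified chi-square has 18.3%, 22.2%, 35.0% and 45.8%. Power is low with either test.

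**The case against.** Protocol section 2 calls the secondary aims exploratory, and the paragraph is about feasibility and satisfaction. Fisher's test is valid, keeps its size below 5%, and is used elsewhere in the SAP for safety proportions. In a small steroid subgroup an exact test is a reasonable choice. The SAP is the more detailed text, so Fisher may be what was intended. SAP 3.3 also requires the analytic plan to be agreed before the final analyses, which limits the room for a choice made after seeing results.

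Most of this stands, and it keeps the point minor. It does not remove the contradiction: both texts are current, no reason is given for the difference, and an agreement step helps only if it settles which test is used.

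A reader might also infer that the SAP loses power because it drops the randomisation stratum. The figures do not support that: at stratum odds ratios up to 2 the unstratified chi-square has essentially the same power as CMH. Nor does protocol 8.4.2 say that its CMH test is stratified by biologic use. It lists no strata, and SAP 5.5.2 speaks only of treatment strata. Biologic use is an inference from protocol 3.3, though a natural one.

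**Conclusion.** The point holds as an inconsistency between protocol and SAP, with a small power cost as a secondary matter. On the borrowed 40% v 60% at 97 per arm, Fisher's power is 76.4% against about 81–82% for uncorrected CMH at stratum odds ratios of 1 to 3, and nearly all of the gap is Fisher's conservatism. The stratum would matter by itself only if biologic use were strongly prognostic, for which the documents give no figure. The gain also depends on CMH being run without continuity correction, which the documents do not specify.

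It would be too strong to say that a powered objective is compromised: no power is claimed for these outcomes. The 97-per-arm figures do not carry over to the steroid subgroup or to the repeat analysis among week-6 remitters, both of which are smaller and of unknown size.

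**What to change.** Before any arm-level analysis, change the sentence in SAP 5.5.2 to match protocol 8.4.2. Specify the CMH test without continuity correction, stratified by biologic use at randomisation, with an exact stratified version where expected counts are sparse, as is likely in the steroid subgroup. Because 8.4.2 does not list the strata, state them there too. If the study team prefers Fisher's test, it should give the reason and amend 8.4.2 so that one test remains.

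The cost is about one sentence in each text. The small downside is that the actual size of the uncorrected test can slightly exceed 5% (5.2% at a 50% null rate for the unstratified chi-square at 97 per arm), which is tolerable for exploratory outcomes.

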## **2 Study Objectives**

This RCT is designed to address the following primary aim and a number of secondary aims which are considered exploratory in nature:

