## 8.2 Secondary Endpoints

### Markers of inflammation

We will compare the proportion of patients who achieve reduction in FCP to less than 250ug/g and by greater than 50% from baseline. Fecal concentration of calprotectin, a calcium binding protein found in neutrophilic granulocytes, will be measured by LabCorp. FCP concentration is correlated with endoscopic findings of mucosal inflammation and decreases following initiation of medications in active CD. There is no single standard to define mucosal healing with FCP; a recent meta-analysis identified 250 µg/g as the optimal cut point for endoscopically defined inflammation among patient with IBD. There are a number of important reasons to measure FCP in this study. From the patient's perspective, FCP predicts the risk of recurrence of symptoms for those who have achieved clinical remission through medical or surgical therapy. Equally as important, to achieve optimal adoption of dietary strategies into the management of CD will require convincing treating physicians of the effectiveness of the diet. Increasingly, physicians are demanding evidence that CD treatments improve inflammation in addition to symptoms. Thus, FCP is a biomarker that predicts an important outcome for patients and for physicians it can be used to document reduction in mucosal inflammation.

We will use hsCRP as a marker of systemic inflammation. We can compare the proportion of patients who have hsCRP below the upper limit of normal and mean levels of hsCRP as outcome measures.

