**Change from baseline stratified by treatment arm:** For continuous outcome measures, such as sCDAI, PRO2, PRO3, and FCP, we will compare the week 6 and week 12 values to the baseline value using the Wilcoxon sign rank test, a nonparametric paired test. These analyses will be conducted separately for each treatment group. Imputation of missing data for this analysis will assume the worst case scenario that the outcome measure was worse during follow-up than at baseline. (Note that approach to missing data for other analyses are described below).

**Approach to missing data (PCORI Methodology Standard MD1-5):** Our study design will minimize missing data by requiring participants to continue to provide data and samples in order to continue to receive the study diets without cost. In addition, we will employ reminder methods that were developed in our current CCFA Partners RCT and will collect symptoms daily, but have documented that less frequent data collection is adequate. It is possible that missing follow-up data will be more common among participants who did not have reduced symptoms, particularly those whose symptoms worsened. There are several approaches to missing data in clinical trials. Complete case analysis violates the principle of

intention to treat and as such will not be employed. For continuous measures, last observation carried forward (LOCF) is the most commonly used, but it is not necessarily the most conservative. Baseline observation carried forward (BOCF) may be more appropriate, particularly in circumstances where the outcome would be expected to return to the baseline level if the treatment is discontinued. The European Medicines Agency recommends picking the most conservative approach depending on the individual trial, favoring a responder analysis (i.e. converting continuous variables to dichotomous variables) and categorizing all dropouts as treatment failures. We will use this approach in analyses for aims 1 and 2. For the continuous variables in the secondary outcomes, we will use BOCF as the most conservative approach. Sensitivity analyses will compare results of our BOCF analysis with that obtained using LOCF or multiple imputation methods. All results will be interpreted and reported after taking into account the results of the sensitivity analyses, applying the principle put forth by the EMA to not favor the “experimental” arm, which in this RCT would be the SCD.

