### 5.5.1.2. Secondary Endpoints

#### 5.5.1.3. Reduction in fecal calprotectin

We will compare the proportion of patients who achieve reduction in FCP to less than 250mcg/g and by greater than 50% from baseline. Fecal concentration of calprotectin, a calcium binding protein found in neutrophilic granulocytes, will be measured by LabCorp Diagnostics. FCP concentration is correlated with endoscopic findings of mucosal inflammation and decreases following initiation of medications in active CD. There is no single standard to define mucosal healing with FCP; a recent meta-analysis identified 250 µg/g as the optimal cut point for endoscopically defined inflammation among patient with IBD. **Participants with a baseline FCP less than 250mcg/g will be excluded from this analysis.**

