### **5.5.2. Statistical analysis for primary and secondary outcome measures**

The primary analysis will compare the proportion of patients who achieve a symptomatic remission (aim 1) and reduction of inflammation (aim 2) at week 6 using the Cochran-Mantel-Haenszel (CMH) chisq test, which is equivalent to the score test derived from the conditional logistic regression with treatment

strata as the conditioning factor. All patients who are withdrawn or lost to follow-up prior to week 6 will be considered treatment failures. The MSD will be considered the reference group for all analyses. Although randomization should minimize unbalance between the groups, it is still possible that unbalance may occur. As such, we will use stratified analyses and conditional logistic regression analysis to adjust for potential unbalance between the two groups as observed in the descriptive analyses. Age, sex, smoking status, duration of CD, presence of disease involving the colon and/or rectum, use of corticosteroids during the trial, current use of biologic therapy, and current use of immunomodulator therapy will be examined individually for potential confounding of the main outcome using logistic regression analysis. All variables that affect the crude estimate of the relative risk of effectiveness by 10% or greater will be included in the final model.

Stratified analyses will be used to assess for treatment effect heterogeneity based on the following variables: duration of CD (as EEN appears to work better in newly diagnosed patients), presence of colonic and/or rectal disease (EEN has been hypothesized to work better in patients with only small bowel disease), and use of corticosteroids during the trial (these patients may have more severe disease). We will use the logistic regression models to look for evidence of treatment-covariate interactions. Although pre-specified, we have not powered the study for these subgroup analyses and as such they will be considered hypothesis generating. Therefore, we will report the overall results as well as results for each subgroup. We note that the strongest a priori hypothesis for treatment effect heterogeneity is with the presence or absence of inflammation. We hypothesize that the SCD may appear relatively more effective among those patients without active inflammation than among those with confirmed active inflammation at baseline.

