Approach to missing data: It is possible that missing follow-up data will be more common among participants who did not have reduced symptoms, particularly those whose symptoms worsened. There are several approaches to missing data in clinical trials. Complete case analysis violates the principle of intention to treat and as such will not be employed. For continuous measures, last observation carried forward (LOCF) is the most commonly used, but it is not necessarily the most conservative. Baseline observation carried forward (BOCF) may be more appropriate, particularly in circumstances where the outcome would be expected to return to the baseline level if the treatment is discontinued. The European Medicines Agency recommends picking the most conservative approach depending on the individual trial, favoring a responder analysis (i.e. converting continuous variables to dichotomous variables) and categorizing all dropouts as treatment failures. We will use this approach in analyses for aims 1 and 2. For the continuous variables in the secondary outcomes, we will use BOCF as the most conservative

approach. Sensitivity analyses will compare results of our BOCF analysis with that obtained using LOCF or multiple imputation methods. All results will be interpreted and reported after taking into account the results of the sensitivity analyses, applying the principle put forth by the EMA to not favor the “experimental” arm, which in this RCT would be the SCD.

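### sCDAI, PRO2, PRO3 and FCP on their original scales are tested only against baseline within each arm, so the between-diet difference on those scales is never estimated (minor, exploratory)

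*Combined protocol and SAP*

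**What the plan says.** **Original scale.** Protocol 8.4.2, on change from baseline by arm, says for sCDAI, PRO2, PRO3 and FCP: "we will compare the week 6 and week 12 values to the baseline value using the Wilcoxon sign rank test". SAP 5.5.2 repeats this and adds: "These analyses will be conducted separately for each treatment group". Missing values in these tests are imputed on the assumption that "the outcome measure was worse during follow-up than at baseline".

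**Between diets.** The same measures are compared between arms only as proportions:
- sCDAI below 150 (SAP 5.5.1)
- FCP below 250 mcg/g with a fall of more than 50% (SAP 5.5.1.3)
- PRO2 and PRO3 cut-points, or a fall equivalent to 100 CDAI points (SAP 5.5.1.3.3)

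For the FCP responder analysis, "Participants with a baseline FCP less than 250mcg/g will be excluded from this analysis".

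**hsCRP.** Protocol 8.2 says: "We can compare the proportion of patients who have hsCRP below the upper limit of normal and mean levels of hsCRP as outcome measures". No test is named for the means. SAP 5.5.2 handles hsCRP as it handles FCP.

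**Other continuous scores.** PROMIS, RADAI, RAPID3 and BASFI are compared between arms (SAP 5.5.2 and 5.5.3). They are adjusted for baseline only if a meaningful baseline difference or confounding is seen, and no threshold is given.

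**Framing.** Protocol section 2 describes "a number of secondary aims which are considered exploratory in nature". SAP 5.5.2 says: "The MSD will be considered the reference group for all analyses".

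**The concern.** The stated objectives compare two diets, and a test run inside one arm has no reference group. If the plan is followed as written, the only results on the score scale will be two separate sets of p-values against baseline. They cannot say which diet did better, or by how much.

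A within-arm fall is also hard to read by itself. Participants enter because their sCDAI exceeds 175, so part of any later fall may be regression to the mean. That part is expected equally in both randomised arms, and only a between-arm contrast removes it.

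For FCP, the one planned between-diet comparison also leaves out participants with baseline below 250 mcg/g. No FCP comparison between diets therefore covers everyone randomised.

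What is at stake is the interpretability of exploratory results, not the primary conclusion.

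**Working it through.** **1. The plan's own figure.** Inputs from SAP 5.2: 40% vs 60%, two-sided 5%, 80% power, chi-square test.

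n per arm = [1.96 × √(2 × 0.5 × 0.5) + 0.8416 × √(0.4 × 0.6 + 0.6 × 0.4)]² / 0.2² = (1.386 + 0.583)² / 0.04 = 96.9, that is 97.

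The sample size reproduces. It is built on the binary endpoint, and nothing below alters it.

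**2. What two within-arm tests can show.** Suppose both arms have the same true change and each within-arm test has power p. The arms are independent, so exactly one is significant with probability 2p(1-p):
- p = 0.50: 2 × 0.50 × 0.50 = 50%
- p = 0.80: 2 × 0.80 × 0.20 = 32%
- p = 0.90: 2 × 0.90 × 0.10 = 18%
- p = 0.998: 2 × 0.998 × 0.002 = 0.4%

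For a paired comparison in 97 people, p is approximately Φ(d√97 − 1.96), where d is the mean change divided by the SD of change. This gives 0.50 at d = 0.2, 0.80 at d = 0.285 and 0.998 at d = 0.5.

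**3. Where this trial is likely to sit.** The documents give no SD or test-retest correlation, so settings must be assumed. Three were simulated with no diet effect: source mean/SD/reliability of 180/70/0.60, 215/65/0.675 and 250/60/0.75, selected on sCDAI between 175 and 400. With regression to the mean as the only source of change, average falls are 20.9, 9.4 and 2.8 points, and sCDAI remission is about 16%, 7% and 2%. SAP 5.2 tabulates 10% to 40% for the Mediterranean arm.

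A common shift was then added to both arms to reach the upper tabulated rates:
- With no missing data, discordant results are at or near 0% at both 30% and 40% remission.
- With 5% or 10% missing at random and imputed as worsening, they stay at about 1% or below, except for one cell at about 7% (first setting, 30% remission, 10% missing, imputed at the largest observed change in the arm). That imputation size is an assumption, because the plan does not say how much worse a missing value should be.

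**4. Even concordant results do not compare the diets.** Both arms can be significant while one diet lowers the score far more than the other. No planned step estimates that difference.

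**5. PRO3 and sCDAI.** SAP 5.5.1.1 gives sCDAI = 44 + (7/d) × (2ΣL + 5ΣA + 7ΣW), where d is here the number of days. If PRO3 uses the CDAI weights on daily means, PRO3 = 2L̄ + 5Ā + 7W̄, and so sCDAI = 44 + 7 × PRO3. An ANCOVA on one is then the same test as on the other.

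SAP 5.5.1.3.3 describes weighted measures but prints formulas without weights. Unweighted, pain (at most 3) and wellbeing (at most 4) add at most 7, so the cited PRO3 value of 53 would need 53 − 7 = 46 stools a day. On the weighted reading, the cited PRO3 fall of 14 is 7 × 14 = 98 sCDAI points, close to the 100 CDAI points it represents. The cut-points therefore fit the weighted version, and the text needs reconciling.

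**6. What a direct comparison would deliver.** At 97 per arm and 80% power, the detectable difference is (1.96 + 0.84) × √(2/97) = 0.40 SD. With an assumed baseline/follow-up correlation of 0.5, it is 0.40 × √(1 − 0.25) = 0.35 SD.

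**The case against.** **The dichotomised analyses are deliberate.** The missing-data text prefers a responder analysis with dropouts counted as failures, and says: "We will use this approach in analyses for aims 1 and 2". The minimum important difference in SAP 5.2 is set on remission rates. A reader might infer that some objective has no between-diet test. The documents do not support that: symptoms, FCP, hsCRP, PROMIS, joint scores and diet continuation are all compared between arms in some form. This part of the objection stands, and it is why the point is minor.

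**The disputed paragraph answers a within-arm question.** A reader might infer that the plan will rank the diets by which arm reaches significance. The plan never says so, and its secondary aims are declared exploratory. This also stands.

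**The BOCF rule may imply a between-arm continuous analysis.** SAP 5.5.2 applies baseline observation carried forward to continuous secondary outcomes. That is a rule for missing values. It names no contrast for these four measures, and the signed-rank tests have their own separate imputation. If a between-arm analysis was intended, it still has to be written down.

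**Mean hsCRP is named.** It is a different marker, offered as something that can be compared, with no method. It does not fill the gap.

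**Conclusion.** The point holds as a minor, exploratory gap. On their original scales, sCDAI, PRO2, PRO3 and FCP are never compared between diets. Two p-values against baseline cannot stand in for that comparison, and regression to the mean contributes to both. The primary CMH analysis and the sample size are untouched.

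A reader might go further and infer that the within-arm tests would often single out one diet by chance. That can be made to appear by assuming that almost nobody improves beyond regression to the mean. Two of the three settings above then imply remission below the SAP's lowest tabulated rate of 10%. At 30-40% remission, discordance is near zero in the settings checked, with the one exception noted. A cohort entering only just above 175 would improve less at a given remission rate, so near zero is not guaranteed. The logical point needs none of these assumptions.

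The conditional baseline adjustment of PROMIS, RADAI, RAPID3 and BASFI is a related weakness, because it leaves the choice of model until the data have been seen.

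**What to change.** In SAP 5.5.2 and protocol 8.4.2:
- Add an exploratory between-arm ANCOVA at weeks 6 and 12 for sCDAI, PRO2, log FCP and log hsCRP. Include all randomised participants, without the baseline FCP exclusion, and adjust for baseline value and the randomised biologic stratum.
- Report the SCD minus MSD difference (a ratio for the log measures) with a 95% confidence interval. Use the plan's BOCF rule, with multiple imputation as sensitivity analysis.
- Keep the responder analyses unchanged, and present within-arm change as descriptive.
- Reconcile the weighted description and the unweighted formulas in SAP 5.5.1.3.3 first. If PRO3 carries the CDAI weights, do not add a separate PRO3 model.

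In SAP 5.5.2 and 5.5.3, adjust PROMIS, RADAI, RAPID3 and BASFI for baseline unconditionally. The reference to week 8 in 5.5.3 is a separate clerical correction, since these measures are collected at 0, 6 and 12 weeks.

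**Cost.** Wording and modest programming on data already collected, with no extra participants. Four outcomes at two visits make eight more comparisons. With no diet difference, 8 × 0.05 = 0.4 would be expected below p = 0.05, so they should be labelled hypothesis-generating, without multiplicity control.
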